4.2 Study Design

Study 111-206 is a phase 2 stratified randomized, double-blind, placebo-controlled clinical trial of vosoritide in infants and younger children with a diagnosis of ACH.

Subjects aged ≥ 6 months to < 60 months old who have documented ACH confirmed by genetic testing; at least a 6-month period of pretreatment growth assessment in Study 111-901 immediately before study entry; and who meet the study eligibility criteria, will participate. Eligible subjects ranging from 0 months to < 3 months old may enroll directly into 111-206 and have a minimum of 3 months of pre-treatment observation prior to commencing treatment with investigational product or may enroll in 111-901 for a minimum of 3 months of pretreatment growth assessment immediately before roll-over to 111-206.

Approximately 70 subjects will be enrolled at approximately 10-15 clinical centers worldwide.

Subjects will be enrolled into 3 age cohorts based on age at study screening starting with the eldest population. Within Cohorts 1 and 2, subjects will be stratified by age:

- Cohort 1 – children aged ≥ 24 to < 60 months ($n \geq 30$ total: 3 sentinel subjects who receive vosoritide, and at least 27 additional subjects randomized 1:1 to treatment or placebo control), stratified by age (≥ 24 months to < 36 months and ≥ 36 months to < 60 months)
- Cohort 2 – children aged ≥ 6 to < 24 months ($n \geq 20$ total: 3 sentinel subjects who receive vosoritide, and at least 17 additional subjects randomized 1:1 to treatment or placebo control), stratified by age (≥ 6 months to < 15 months and ≥ 15 months to < 24 months)

- Cohort 3 – children aged 0 to < 6 months (n ≥ 20 total: 3 sentinel subjects who receive vosoritide, and at least 17 additional subjects randomized 1:1 to treatment or placebo control). Treatment begins at ≥ 3 months to < 6 months after 3 months of observation.

[figure not shown]
Sentinel subjects from each cohort will be enrolled, treated with vosoritide, and studied for short-term safety and PK data. After the sentinel data are evaluated within a cohort additional recruited subjects will be randomized to receive vosoritide or placebo subcutaneous daily (1:1 ratio) for 52 weeks.

As subjects age on study, they will be administered the dose determined to be appropriate for their current age as follows:

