4.3 Study Populations

Subjects aged 0 to < 60 months old, with documented ACH confirmed by genetic testing, and who meet the study eligibility criteria will participate.

For additional criteria for selection of study population, please refer to inclusion and exclusion criteria for the protocol.

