15.1.2 Events of Interest

Events of interest (EOI) will be summarized by PT separately by cohort and overall by treatment group using format as specified in [Table 5.4](#). For those AEs that occurred more than once during the study, the maximum severity will be used to summarize the AEs by severity.

The following are identified as events of interest:

Injection site reactions (ISR)

- TEAEs with a MedDRA High Level Term (HLT) of “Injection site reaction”.

Hypotension

- TEAEs with PT: Blood pressure ambulatory decreased, Blood pressure decreased, Blood pressure diastolic decreased, Blood pressure orthostatic decreased, Blood pressure systolic decreased, Blood pressure systolic inspiratory decreased, Diastolic hypotension, Hypotension, Orthostatic hypotension.

Heart rate change

- TEAEs with a PT: Atrial tachycardia, Postural orthostatic tachycardia syndrome, Rebound tachycardia, Sinus tachycardia, Supraventricular tachycardia, Tachycardia, Tachycardia paroxysmal, Ventricular tachycardia, Bradycardia.

Hypersensitivity SMQ

- TEAEs with a PT included in the MedDRA hypersensitivity SMQ

Algorithmic Anaphylaxis SMQ (with sponsor-defined time restrictions)

- TEAEs with a PT included in the MedDRA anaphylactic reaction SMQ, with an additional time restriction: a narrow scope PT within 48 hours of a dose, or two broad scope PTs from different classes where both PTs are within 48 hours of the same dose.

Fractures

- TEAEs with a PT containing the term “fracture” and also PTs of Bone fragmentation, Bone fissure, Scapulothoracic dissociation and Flail chest

Slipped Capital Femoral Epiphysis (SCFE)

- TEAEs with a PT: Epiphyseal disorder, Epiphyseal injury

Avascular necrosis and osteonecrosis

- TEAEs with a PT: Osteonecrosis, Osteonecrosis of jaw, Osteonecrosis of external auditory canal, Necrosis ischaemic

Events of interest will be summarized as follows:

- Incidence and exposure-adjusted event rates of ISR events by PT
- Incidence and exposure-adjusted event rates of hypotension by PT
- Incidence and exposure-adjusted event rates of heart rate change events by PT
- Incidence and exposure-adjusted event rates of hypersensitivity (SMQ)
- Profile of ISRs
- Profile of hypotension
- Profile of heart rate change events

Profile summaries include: highest CTCAE grade, number of events per subject, time from first dose to first event onset, duration of events (days), action taken with study treatment, outcome of events.

Listings:

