Shift tables (Diastolic BP <30mmHg, Diastolic BP \geq 30mmHg) from pre-dose to same-day lowest post-dose value category (Diastolic BP <30mmHg, Diastolic BP \geq 30mmHg) will be generated by visit and for overall (each subject meeting criteria at any time in the study will be counted only once) for both sentinel subjects and randomized subjects.

Shift tables (Systolic BP < (70mmHg plus 2 x Age), Systolic BP \geq (70mmHg plus 2 x Age)) from pre-dose to lowest same-day post-dose value category ((Systolic BP < (70mmHg plus 2 x Age), Systolic BP \geq (70mmHg plus 2 x Age))) will be generated by visit and for overall (each subject meeting criteria at any time in the study will be counted only once). Subject's age used in this calculation is the integer value.

A listing of vital sign data will also be provided.

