15.5 Electrocardiogram

Electrocardiogram (ECG) data are recorded at Screening, Day 1, Day 8, Week 6, Week 13, Week 20, Week 26, Week 39, Week 52, safety follow-up visit, and early termination visit.

ECG assessments are performed in triplicate on Day 1 (pre-dose and post-dose) and on study day visits (post-dose only).

Summaries will be provided over all planned assessments, and repeated with the requirement that all post-dose ECG assessments should occur around the expected time of C_{Max}, i.e., 20-40 minutes post-dose. The mean results of the ECG assessments meeting these criteria will be used for summaries and analyses.

All measures and means of the measures will be included in the listings.

The following ECG results will be summarized and presented separately by cohort and overall by treatment group using format as specified in [Table 5.4](#) at scheduled visits:

- ECG Mean Heart Rate (beats/min)
- QT interval (msec)
- QTcF interval (msec)
- PR interval (msec)

- RR interval (msec)
- QRS Duration (msec)

The following endpoints will be summarized at scheduled visits, and across all time points (using the highest mean QTc value), and presented by cohort and overall by treatment group using format as specified in [Table 5.4](#).

- Percentage of subjects with QTcF >450 to ≤480ms, >480 to ≤500ms, >500 msec

The following endpoints will be summarized at scheduled visits, and across all time points, and presented by cohort and overall by treatment group using format as specified in [Table 5.4](#)

- Percentage of subjects experiencing at least one instance of a (decrease in mean heart rate from pre-dose baseline >25% and a mean heart rate <50 beats/min) post-dose.
- Percentage of subjects experiencing at least one instance of an (increase in mean heart rate from pre-dose baseline >25% and a mean heart rate >100 beats/min) post-dose.

The following endpoints will be summarized across all time points and presented by cohort and overall by treatment group using format as specified in [Table 5.4](#).

- Percentage of subjects with a QTcF increase of 60ms from pre-dose baseline at any time
- Percentage of subjects with QTcF changes from pre-dose baseline of >30 and ≤ 60 msec, or >60 msec at any time

Listings will be provided and ordered by cohort, sentinel/randomized subject, treatment group, and visit:

- All ECG results.
- All ECG results for subjects with a QTc increase of 60msec from pre-dose baseline.

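### The ECG heart-rate decrease row is decided by its fixed limit of 50 beats/min rather than its 25% criterion, so at these ages it can show very little

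*SAP*

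**What the plan says.** Section 15.5 (Electrocardiogram) defines two post-dose heart-rate outlier percentages. Each counts subjects who meet the rule at least once.

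- Decrease: "decrease in mean heart rate from pre-dose baseline >25% and a mean heart rate <50 beats/min".
- Increase: "increase in mean heart rate from pre-dose baseline >25% and a mean heart rate >100 beats/min".

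Both are tabulated at scheduled visits and across all time points, by cohort and overall, in the Table 5.4 layout (sentinel, randomized vosoritide, randomized placebo, all vosoritide treated). The limits of 50 and 100 do not vary with age, and no reason is given for them. Versions 1.1 and 2 of the SAP carry the same rule.

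Section 4.3 gives the population: "Subjects aged 0 to < 60 months old, with documented ACH confirmed by genetic testing". Under Section 4.2 cohort membership follows age at screening, so the oldest children can be almost 6 years old by Week 52.

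Two rules in Section 15.3 (Vital Signs) are built differently. The systolic limit is "70mmHg plus 2 x Age", which moves with age. A 20% fall in diastolic pressure from pre-dose to the same day's post-dose readings is reported on its own, with no absolute limit attached.

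**The concern.** The two parts of the decrease rule are joined by *and*, so the stricter part governs. The 25% figure suggests that moderate falls will be picked up. In a child who starts well above 67 beats/min, the limit of 50 asks for a much larger fall before anything is counted.

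Heart rate change is a named event of interest in Section 15.1.2, where the listed terms end with "Tachycardia paroxysmal, Ventricular tachycardia, Bradycardia". The threshold tables in Section 15.3 cover blood pressure only, so the two ECG rows are the SAP's only threshold-based summary of heart rate. A decrease row at or near zero in both arms could be read as reassurance, when the rule leaves little room for any other result.

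**Working it through.** **Inputs.** The two rules come from Section 15.5 and the age range from Section 4.3. The SAP states no heart-rate range and no expected rate for either row, so there is no figure of its own to reproduce. Pre-dose rates of 80 to 160 beats/min are an assumption, shown across the range.

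**Decrease rule.** For pre-dose rate B, the fall must exceed max(25%, 1 − 50/B). The two parts are equal at B = 50/0.75 = 66.7. Above that, only the limit of 50 matters.

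| Pre-dose rate B | Rate after a 25% fall | Fall needed to be counted |
|---|---|---|
| 80 | 60.0 | 37.5% |
| 90 | 67.5 | 44.4% |
| 100 | 75.0 | 50.0% |
| 120 | 90.0 | 58.3% |
| 140 | 105.0 | 64.3% |
| 160 | 120.0 | 68.8% |

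A fall from 120 to 61 is (120 − 61)/120 = 49.2% and is not counted.

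**Increase rule.** The rise must exceed max(25%, 100/B − 1). The two parts are equal at B = 100/1.25 = 80. At 80 or more, every rise above 25% already passes 100, so the limit removes nobody. Below 80 it still acts: the rise needed is 33.3% at 75 and 42.9% at 70. With an SD of 10 to 15, the share of baselines below 80 is 16–25% at a mean of 90, 2–9% at a mean of 100 and 0.1–2.3% at a mean of 110.

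**How often the decrease rule fires.** This is a simulation under assumed values: baseline SD 13, and percentage change centred on zero. The figures are percentages of single readings.

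| Mean baseline | SD of change | Fall >25% alone | Fall >25% and <50 |
|---|---|---|---|
| 100 | 10% | 0.61 | 0.005 |
| 100 | 15% | 4.81 | 0.183 |
| 100 | 20% | 10.60 | 1.068 |
| 125 | 10% | 0.62 | 0.000 |
| 125 | 15% | 4.86 | 0.007 |
| 125 | 20% | 10.54 | 0.186 |

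The row across all time points counts subjects, not readings. Section 15.5 schedules eight ECG visits from Day 1 to Week 52. If each visit contributes one mean reading, the share of subjects flagged is at most eight times the per-reading figure. At a change SD of 15% that is at most 8 × 0.183 = 1.5% (mean 100) and 8 × 0.007 = 0.06% (mean 125). At an SD of 20% it is at most 8 × 1.068 = 8.5% and 8 × 0.186 = 1.5%. Near zero is therefore a fair description, except where lower baselines meet the widest variability.

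**The case against.** The strongest reply is that little depends on this row. It is descriptive, tied to no hypothesis, and heart rate is well covered elsewhere:

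- Section 15.3 takes vital signs, including heart rate, repeatedly after dosing. It plots pre- and post-dose means by visit, cohort and arm, and lists every value.
- Section 15.5 summarizes "ECG Mean Heart Rate (beats/min") at scheduled visits and repeats the summaries for readings 20 to 40 minutes after dosing. The default statistics in Section 5 include quartiles, minimum and maximum, and all ECG results are listed.
- Section 15.1.2 defines the heart-rate event of interest by adverse-event terms, with incidence, exposure-adjusted rates, a profile and a listing.

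All of this stands. A reader might infer that the ECG table is the objective measure behind the event of interest, or that the safety output would look clean whatever the drug did. The documents support neither. A marked fall would appear in the minimum and in the listings, and the increase row works as a count of rises above 25% at baselines of 80 or more.

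A reader might also infer that the SAP contradicts itself because its systolic limit is age-scaled. It does not. Its diastolic limits (40 and 30 mmHg) and its QTcF limits are fixed at all ages, so fixed limits are not out of line with the rest of the plan.

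Finally, the joint rule may be meant to capture only an extreme event. That is possible, but the SAP does not say so, and a stated 25% criterion that never operates above 66.7 beats/min fits that reading poorly.

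**Conclusion.** The point holds for the decrease row only. Above 66.7 beats/min the limit of 50 replaces the 25% criterion; this is arithmetic and needs no assumption. That the row will be close to zero, and so uninformative, rests on assumed resting rates of 80 to 160 beats/min, which imply a required fall of 37.5% to 68.8%. The effect is strongest at the highest baselines. The limit of 100 in the increase row is a harmless redundancy at baselines of 80 or more, and it is not redundant below that. The efficacy analyses and the other heart-rate outputs are untouched. This is a confined weakness in one safety row, worth correcting because the correction is nearly free.

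**What to change.** In Section 15.5, add a row for the percentage of subjects with a fall of more than 25% from pre-dose baseline without the absolute limit. For symmetry, add the same for a rise of more than 25%. Present both by cohort and arm in the Table 5.4 layout. This follows the form already used for the 20% diastolic fall in Section 15.3. Keep the two fixed-limit rows as secondary. If age-specific limits are wanted as well, the sponsor should choose them and cite the source; none is proposed here.

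The cost is two table rows and no new data. The downside is that more subjects will be flagged in both arms. Section 15.5 specifies pre-dose ECGs for Day 1 and post-dose ECGs only at later visits, so a row measured against the Day 1 value may also pick up some decline in heart rate with age over the year. It should therefore be read against the randomized placebo column and not on its own.

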15.6 HPA Axis Assessments

To address potential effects of vosoritide on activation of the hypothalamic pituitary (HP) axis, assessment of salivary cortisol and serum prolactin levels will be analyzed at baseline, Week 26, Week 52 and early termination visit.

This data will be listed.

15.7 Child Behavior Checklist ([Achenbach, 2000](#))

The Child Behavior Checklist (CBCL) 1.5- 5 years questionnaire is captured at Screening, Week 26, Week 52, and early termination visit.

All summaries will be generated on the Safety Population and include all assessments recorded up to 30 days following treatment discontinuation. Listings will include all reported data.

The CBCL 1.5-5 years old comprise questions addressing symptoms related to mood, behavior issues, and sleep disturbance. It is completed by the parent or primary caregiver.

The CBCL 1.5-5 years old consists of 100 questions, scored on a three-point Likert scale (0=Not True (as far as you know), 1= Somewhat or Sometimes True, 2=Very True or Often True). The time frame for item responses is the past 2 months.

Note: No data is collected from the language scale, as it is supplemental and not required to calculate any of the behavior measures.

The checklist yields scores in the following areas: emotionally reactive, anxious/depressed, withdrawn, somatic complaints, sleep problem, attention problems, and aggressive behavior.

The table in Appendix 25.2 shows how the domains are constructed with regards to the individual questions. The scores for each individual question within a domain are summed to give a domain score.

Each domain score above and total score will be summarized separately by cohort and overall by treatment group using format as specified in Table 5.4 at Baseline, Week 26 and Week 52 as well as change from baseline at Week 26 and Week 52 (where baseline measures exist).

Domain scores and total score will be listed by cohort, sentinel/randomized subjects, treatment group, and subject ID.

15.8 Echocardiogram

Echocardiogram results are only collected at the Screening visit, at safety follow up, and early termination visit if the previous assessment was done more than 3 months prior to early termination and will be listed by cohort, sentinel/randomized subjects, treatment group, and subject ID.

15.9 On-Study Procedures, Interventions and Surgeries

Any procedures, interventions or surgeries that occur on study (post first dose of study treatment) will be captured, along with start and stop date. These will be coded using MedDRA version 24.1 and will be summarized separately by cohort and overall by treatment group using format as specified in Table 5.4, and details provided in a listing.

15.10 Hip Monitoring and Rotation

All hip monitoring clinical assessments, including hip rotation, will be listed by cohort, sentinel/randomized subjects, treatment group, subject ID, and assessment date.

15.11 Body Mass Index and BMI Z-scores

Weight (kg) and standing height are collected at Screening, Day 1, Day 2, Day 3, Day 8, Week 3, Week 6, Week 13, Week 20, Week 26, Week 39, Week 52, and early termination visit.

Standing height are recorded at Screening, Day 1, Week 6, Week 13, Week 26, Week 39, and Week 52.

Body Mass Index (BMI) will be calculated at each visit as:

$$\text{Body Mass Index (kg/m}^2\text{)} = \frac{\text{Weight (kg)}}{\text{Height (m)}^2}$$

In calculation of BMI, in case standing height is not measured and body length is available, a derived standing height will be calculated; refer to Section **Error! Reference source not found.**

Only for subjects aged 24 months or older, each measurement of BMI will be converted to an age-and sex-appropriate standard deviation score (SDS), also referred to as a Z-score, by comparison with reference data available for average stature children from the Centers for Disease Control and Prevention (CDC). The derived height mentioned above for BMI is also used for BMI in the calculation of BMI Z-score.

The absolute values at baseline, each 6-month visit, and change from baseline at each 6-month visits will be summarized and presented separately by cohort and overall by treatment group using format as specified in [Table 5.4](#) for both BMI and BMI Z-Score (again though, BMI Z-score will only be calculated for subjects aged 24 months or older).

All assessments will be listed by cohort, sentinel/randomized subjects, treatment group, subject ID and visit.

15.12 Weight Z-Scores

Weight (kg) is measured at Screening, Day 1, Day 2, Day 3, Day 8, Week 3, Week 6, Week 13, Week 20, Week 26, Week 39, Week 52, and early termination visit.

Each measurement of weight will be converted to an age-and sex-appropriate SDS, also referred to as Z-score, by comparison with reference data available for average stature children from the CDC.

The weight of the subject on Day 1 will be used as the baseline measure, regardless of whether this is recorded pre or post-dose.

The absolute values and change from baseline at scheduled visits will be summarized and presented separately by cohort and overall by treatment group using format as specified in [Table 5.4](#).

All assessments will be listed for by cohort, sentinel/randomized subjects, treatment group, subject ID, and visit.

16 IMAGING SECONDARY ENDPOINT(S)

Imaging will be performed at screening, Week 52, and early termination visit:

Dual energy X-ray absorptiometry of whole body and spine

Anterior-posterior and lateral lumbar spine X-rays

Anterior-posterior X-rays of lower extremities

MRI data will be performed at screening, Week 52, and early termination visit to evaluate the effect of vosoritide on skull and brain morphology, including face, foramen magnum, ventricular, and brain parenchymal dimensions.

All summaries of imaging data and MRI data will be generated on the FAS and presented by cohort and overall by treatment group using the format as specified in [Table 5.4](#).

16.1 Lower Limb X-Rays

For each of the following parameters, the absolute values for both the left and right leg at Baseline and Week 52, and change from baseline at Week 52 will be summarized by cohort and overall by treatment group using the format as specified in [Table 5.4](#):

- Left/Right Femur length (cm)
- Left/Right Fibula length (cm)
- Left/Right Tibia length (cm)
- Left/Right Tibia bowing angle (degrees)
- Left/Right Distance between ankle joint and distal growth plate of fibula (cm)
- Left/Right Lower Extremity (cm)
- Ratio of Left/Right Femur length (cm) to Tibia length (cm)
- Ratio of Left/Right Tibial length (cm) to Fibula length (cm)

In addition, change from baseline in tibial length (y-axis) at Week 52 will be presented on boxplots with a separate box for each leg and treatment group on the x-axis by cohort. Similar plots will also be generated for change from baseline in fibula length.

All assessments will be listed by cohort, treatment group, subject and visit.

16.2 Lumbar Spine X-Rays

Lumbar spine x-rays (AP and lateral views) assessments will be listed by cohort, treatment group, subject and visit.

16.2.1 Vertebral Height

Vertebral heights (anterior, medial, and posterior) will be measured for each individual vertebra (L1, L2, L3, L4, and L5).

The following ratios will be calculated for each individual vertebra (L1, L2, L3, L4, and L5) and reported to 1 decimal place:

- Anterior height (cm) to medial height (cm)
- Anterior height (cm) to posterior height (cm)
- Medial height (cm) to posterior height (cm)

For each of the vertebral height and the above ratios, the absolute values at Baseline and Week 52, and change from baseline at Week 52 will be summarized and presented by cohort and overall by treatment group using the format as specified in [Table 5.4](#).

16.2.2 Transverse Diameter (Interpedicle Distance)

The transverse diameter (interpedicle distance) will be measured for each individual vertebra (L1, L2, L3, L4, and L5).

For each transverse diameter vertebra, the absolute values at Baseline, Week 52, and the change from baseline at Week 52 will be summarized and presented by cohort and overall by treatment group using the format as specified in [Table 5.4](#).

In addition, change from baseline in transverse diameter (y-axis) for each individual vertebra (x-axis) will be presented on a boxplot at Week 52 for each cohort and treatment group.

